One of the potential ways that has shown promise is leukocyte-platelet-rich fibrin (L-PRF), an autologous fibrin clot that has been shown to positively influence postoperative healing cascades.[17] Rich in growth factors, L-PRF improves healing times through accelerated tissue migration at the site of surgery which ultimately reduces inflammation.[18] There have been reports of improved soft tissue healing, increased QoL, and patient reported reduction in pain following the use of L-PRF.[19-21] However, due to conflicting studies regarding the efficacy of L-PRF in comparison to control groups, further investigation is required.[22] Therefore, this prospective cohort study aims to evaluate the relationship between L-PRF, sleep, and perceived QoL on healing in patients undergoing periodontal mucogingival surgery compared to standard surgical intervention.

9.3

Objectives/Specific Aims/Research Questions:

Describe the purpose and objective(s) of the study, specific aims, and/or research questions /hypotheses

Specific Aim 1: Determine if subjects' self-perceived QoL after periodontal mucogingival surgery is influenced by differences in tissues healing with and without L-PRF at the tissue donor site.

Objective 1. Document subjects' perceived QoL pre/post-surgery with QoL questionnaire (pre-surgical, 24 hr, 72hr, one week post operative appointment, two week post-operative appointment).

Objective 2: Measure clinical indicators to determine presence of infection and healing status at one-week post-operative appointment.

Objective 3: Measure clinical indicators to determine presence of infection and healing status at the two-week post-operative appointment.

Specific Aim 2: Determine if tissue healing with and without L-PRF at the tissue donor site after periodontal mucogingival surgery influences quality and/or quantity of sleep before and during the healing phase.

Objective 1: Characterize pre-surgical sleep quality via SQI over a 3-7-day period using a sleep monitoring device for sleep and vital signs.

Objective 2: Characterize post-surgical sleep quality via SQI over a two-week period using a sleep monitoring device.

Objective 3: Measure clinical indicators to determine presence of infection and healing status at the one-week post-operative appointment.

Objective 4: Measure clinical indicators to determine presence of infection and healing status at the two-week post-operative appointment.

9.4 Study Design:

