Pre-Op Appointment: After informed consent is obtained at the pre-op appointment, subjects undergoing mucogingival surgery will be given a sleep monitoring device (SleepImage® Ring 2019, SleepImage, Denver, CO) and will complete a baseline QoL survey (Qualtrics Survey, 2002, Qualtrics, Seattle WA).[11, 23-26] The sleep monitoring app will be downloaded on the subjects' phone and each subject will be trained on the function of the application by the principal investigators. Principle investigators (PI) will assist subjects to download the app and establish an account during the pre-op appointment. Subjects will create an account using their personal email, date of birth, and first/last name which will generate an unidentifiable subject number, which will be tracked in a secured file (Master Key of identifiable PII) accessible only by the PIs. The subject will accrue no fees upon creation of the account. Subjects will be instructed to contact the PIs with any malfunction or questions regarding the use of the application. The application will record sleep quality index (SQI), sleep efficiency, fragmentation, latency, duration, sleep opportunity and periodicity. This specific study will only utilize the SQI as the primary outcome variable. Subjects will be instructed to wear the device nightly throughout the study. The subject will be instructed to complete the same QoL questionnaire at 24 hours, 72 hours, as well as at the one week and two week post-operative appointments (study will last a total of three weeks).

Surgical appointment:

Blood (40 mL) will be collected at the beginning of the surgical appointment and spun using a horizontal centrifuge for the group receiving L-PRF (Horizon 6, horizontal PRF centrifuge machine, 2022, Drucker Diagnostics, Port Matilda, PA). L-PRF (test group selected via computerized randomization scheme with allocation 1:1 ratio) will be made from the blood collected as per manufacturer's protocol (4 vials of blood, centrifuged at 700g for 16 minutes at room temperature). Though some providers choose to use PRF routinely in mucogingival periodontal surgeries, for this study it will be for research purposes. Subjects not receiving L-PRF will have mucogingival surgery initiated without a prior blood draw.

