Statistical Analysis: All dichotomous or categorical variables will be presented initially as counts with percentages. Any analysis looking at two dichotomous or categorical variables will be compared using Chi-Square test. Continuous outcome variables will be initially assessed for normality by the Shapiro-Wilks test and then presented as means with standard deviations if normally distributed; independent t-test will be used determine any group differences between such variables (i.e. post-surgery – pre-surgery) or an ANOVA for three or more normally distributed variables. Otherwise, non-normally distributed outcomes will be presented as median and interquartile range (IQR) and analyzed using Wilcoxon Sign-Ranked Test or Mann-Whitney U Test for three or more variables. To test the relationship between QoL, sleep quality, healing outcomes, and intervention use, adjusted linear regression will be performed with guidance from a biostatistician. Significance will be set to $p < 0.05$. Any additional data collection or analyses will be determined in coordination and consultation with other investigators and the biostatistician through Qualtrics® and SleepImage® software. Subgroup analyses will be conducted in subjects with the following conditions: anxiety or depressive medications, smoking, sleep apnea, pulmonary disease, diabetes, autoimmune disorders, and chronic pain management as well as subject age and sex.

11.2 Sample Size:

Sample Size Estimation/Power Analysis:

The required sample size is 80, 40 subjects will receive the standard treatment and 40 the experimental intervention. It was calculated by using a priori analysis to provide a power of 80%, false positive rate of 5%, a 10% margin of error, and a 10% calculated dropout rate.

11.3 Total number of subjects requested (including records and specimens):

11.4 If you are recruiting by study arm, please identify the arms of the study and how many subjects will be enrolled in each arm

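### The rank tests for non-normal outcomes are mis-assigned: Mann-Whitney U is tied to three or more samples, and no rank test is correctly assigned to L-PRF versus control

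*Combined protocol and SAP*

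**What the plan says.** Sections 11.1 and 11.6 carry the same rule. Continuous outcomes are checked with a Shapiro-Wilk test. If they look normal, an "independent t-test will be used determine any group differences between such variables", "or an ANOVA for three or more normally distributed variables". If not, they are summarised by median and IQR and "analyzed using Wilcoxon Sign-Ranked Test or Mann-Whitney U Test for three or more variables". The t-test clause gives the post-surgery minus pre-surgery difference as its example: "any group differences between such variables (i.e. post-surgery". Neither section names Kruskal-Wallis, Friedman or any repeated-measures method. Both also plan an adjusted linear regression relating QoL, sleep quality, healing and the intervention, and both send categorical variables to chi-square.

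The design these tests must serve is as follows:

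- **Arms.** Section 10.1 has the "test group selected via computerized randomization scheme with allocation 1:1 ratio", and section 11.2 says "40 subjects will receive the standard treatment and 40 the experimental intervention".
- **Aims.** Both aims in section 9.3 ask about healing with versus without L-PRF.
- **QoL times.** Section 9.3 lists "pre-surgical, 24 hr, 72hr, one week post operative appointment, two week post-operative appointment".
- **Sleep.** Section 10.1 states: "This specific study will only utilize the SQI as the primary outcome variable".
- **Healing.** It is scored on a 1 to 5 index at the post-operative visits only.

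**The concern.** The two sentences run in parallel: one test for two groups and another for three or more, first for normal data and then for the remainder. Read that way, the signed-rank test replaces the independent t-test and Mann-Whitney U replaces ANOVA. Signed-rank needs pairs, and two separately randomized arms have none. Mann-Whitney U takes two samples, and so cannot do the work of ANOVA.

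At stake is the treatment comparison for any outcome that fails the normality check, possibly including SQI, the primary outcome variable. An analyst who follows the text must either pair unrelated subjects, test each arm separately, or depart from the plan after the data are in.

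**Working it through.** **1. The plan's own figure.** The total of 80 cannot be reproduced, because section 11.2 gives no endpoint, effect size or SD. It is consistent with 36 evaluable per arm: 36 / (1 − 0.10) = 40. I use 36 per arm below as an assumption. The standardized difference detectable with 80% power at two-sided 5% is then (1.960 + 0.842) × √(2/36) = 0.66. I use 0.66 as the assumed shift. None of this affects whether the tests are mis-assigned.

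**2. The certain half.** Mann-Whitney U is defined for two independent samples. With two arms, three or more can arise only from repeated times (five for QoL, in the same subjects) or from a covariate with several levels. The test fits neither. If it were forced onto independent groups as unadjusted pairwise tests, simulated familywise error (2,000 runs) is 10.6% for three groups and 29% for five, against 4.7% and 4.9% for Kruskal-Wallis. The plan does not say it would do this; the figures only show what one improvisation would cost.

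**3. Reading A: signed-rank compares the arms.** With 36 against 34 subjects the paired routine stops with an error. With equal arms a pairing must be invented. Results of 5,000 runs per row, where normal means SD 1, lognormal means log-scale mean 0 and SD 1, and the shift is added on the raw scale:

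| Data | Shift | Mann-Whitney rejects | Signed-rank rejects | Signed-rank decision flips on re-pairing |
|---|---|---|---|---|
| Normal | 0 | 4.6% | 4.7% | 3.0% |
| Normal | 0.66 | 77% | 76% | 8.3% |
| Lognormal | 0 | 4.9% | 4.7% | 3.3% |
| Lognormal | 0.66 | 84% | 60% | 13.4% |

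Type I error holds. The harm is a result that depends on row order and, on skewed data, a loss of 84 − 60 = 24 points of power. Skewed data are what this branch of the plan is for.

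**4. Reading B: signed-rank tests post minus pre within subjects.** For that contrast the test is valid: its simulated type I error at n = 36 is 5.0% to 5.6% for correlations from 0 to 0.7. But it does not compare arms. If both arms truly change by the same amount and each within-arm test has power w, exactly one arm is significant with probability 2w(1 − w):

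- w = 0.50: 2 × 0.50 × 0.50 = 50%
- w = 0.80: 2 × 0.80 × 0.20 = 32%

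A simulation with a common change of 0.5 SD (3,000 runs) gave w = 0.813, for which the formula gives 2 × 0.813 × 0.187 = 30%. The simulated rate was also 30%. Mann-Whitney U between arms on the same data rejected in 5.2%, as it should under no L-PRF effect.

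**5. Side by side.** Reading A assigns a paired test to unpaired arms. Reading B assigns no rank test to the arms. Under both, the one named test that would suit the arm comparison is tied to three or more.

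**The case against.** The strongest reply is that the text never says signed-rank is for comparing arms. That is inferred from the sentence structure, and the post-minus-pre example points to a contrast for which signed-rank is right. This stands as far as it goes. It rescues signed-rank for within-subject change, but leaves the question in the aims without a rank test.

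A reader might infer that every non-normal outcome would be tested by an invalid procedure. The documents do not support that:

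- Signed-rank is valid for within-subject change, and even arbitrary pairing across arms keeps type I error near 5%.
- Mann-Whitney U is named, though for the wrong case.
- The adjusted regression also covers QoL, sleep and healing. Its model and covariates are not specified, however, and it does not replace the stated group tests.
- The plan does not say whether the 1 to 5 healing index counts as continuous or categorical. If categorical, it goes to chi-square and never reaches this branch. For SQI and QoL, non-normality is possible but not established.

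It is also fair to say that the within-arm discordance misleads only if someone reads one significant arm and one non-significant arm as an L-PRF effect. The plan does not propose that reading. The figure shows why the plan should rule it out.

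**Conclusion.** The rule is wrong as written in both sections. That Mann-Whitney U cannot serve three or more samples is certain. That signed-rank is misplaced rests on the parallel wording. On the alternative reading the defect changes form but remains: no rank test is correctly assigned to the randomized comparison.

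The size depends on the reading. Across arms, decisions flip in about 8% to 13% of trials with a true effect, and power drops from 84% to 60% on lognormal data but only from 77% to 76% on normal data. Within arms, exactly one arm is significant in 32% of trials at 80% within-arm power and in 50% at 50%, with no difference between arms. These figures rest on assumptions that the documents do not fix: 36 evaluable per arm, the 0.66 and 0.5 shifts, and the normal and lognormal shapes. Type I error inflation from pairing the arms is not part of the finding.

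**What to change.** In sections 11.1 and 11.6, replace the non-parametric sentence with an assignment by purpose:

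- **L-PRF versus control:** Mann-Whitney U (Wilcoxon rank-sum), applied to post-minus-pre change where a baseline exists (SQI, QoL) and to the post-operative value otherwise (healing index).
- **Within-subject pre/post change:** Wilcoxon signed-rank, as description and not as the test of L-PRF.
- **Three or more independent groups:** Kruskal-Wallis.
- **The five QoL times:** a mixed model with arm, time and arm-by-time terms. Friedman would not do, because it tests time within subjects and does not compare arms.
- **Healing index:** state that the 1 to 5 score is analysed as ordinal by Mann-Whitney U, so that it is not left between the chi-square and continuous rules.

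The cost is a wording change in two sections, made before analysis. It changes no data collection and no subject numbers.

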After informed consent is obtained at the pre-op appointment, subjects undergoing mucogingival surgery will be given a sleep monitoring device (SleepImage® Ring 2019, SleepImage, Denver, CO) and will complete a baseline QoL (Qualtrics XM®, 2002, Qualtrics, Seattle WA) [11, 23-26] The sleep monitoring app will be downloaded on subjects' phones and each subject will be briefed on the function of the application. Subjects will be instructed to wear the device nightly throughout the study. The subject will be instructed to complete the same QoL questionnaire at 24 hours, and 72 hours, as well as at the one-week and two-week post-operative appointments. The subjects' medical history will be coded and the following conditions will be noted: L-PRF, no-PRF, type of surgery, type of sedation, experience level of clinician, length of surgery, size of harvest, smoking, diabetes. Subjects' age and sex will also be documented. All of these parameters are reflected in the total data collection sheet. The mucogingival surgery will have been recommended and accepted by subjects as the standard of care.

At the follow-up appointments, subjects will complete the one- and two-week questionnaires to evaluate their perceived QoL since the time of the surgical intervention (see questionnaire). The healing of the palatal harvest site will be evaluated by two calibrated clinicians using the Landry et al. healing index on a scale of 1-5 (see data collection sheet).[18] The provider will complete a routine post-operative examination which includes visualizing and palpation of the surgical area for swelling, removal of sutures, evaluation of pain, noting any purulence upon palpation, noting any tenderness upon palpation of lymph nodes, and temperature obtained to indicate yes/no for infection. This data collection is considered standard of care. Data from the QoL surveys will be analyzed using Qualtrics® data system. Sleep data will be extracted and analyzed in the SleepImage® portal.

10.3 At any point in the study, will you request, use, or access health information in any form, including verbal, hard copy and electronic?

☒ Yes ☐ No

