11.5 Please provide a justification for your sample size

Sample Size Estimation/Power Analysis:

The required sample size is 80, 40 subjects will receive the standard treatment and 40 the experimental intervention. It was calculated by using a priori analysis to provide a power of 80%, false positive rate of 5%, 10% margin of error, and 10% calculated drop-out rate.

11.6 Data Analysis Plan: Complete description: Background, Objectives, Design, Step by Step how the project is going to be done, Data analysis plan:

Statistical Analysis: All dichotomous or categorical variables will be presented initially as counts with percentages. Any analysis looking at two dichotomous or categorical variables will be compared using Chi-Square test. Continuous outcome variables will be initially assessed for normality by the Shapiro-Wilks test and then presented as means with standard deviations if normally distributed; independent t-test will be used to determine any group differences between such variables (i.e. post-surgery – pre-surgery) or an ANOVA for three or more normally distributed variables. Otherwise, non-normally distributed outcomes will be presented as median and interquartile range (IQR) and analyzed using Wilcoxon Sign-Ranked Test or Mann-Whitney U Test for three or more variables. To test the relationship between QoL, sleep quality, healing outcomes, and intervention use, adjusted linear regression will be performed with guidance from a biostatistician. Significance will be set to $p < 0.05$. Any additional data collection or analyses will be determined in coordination and consultation with other investigators and biostatistician.

12.0
Participant Information
12.1 Subject Population:

Sample population: 80 non-emergency subjects (active-duty, retired, dependents, retired-dependents) at the USAF Graduate Periodontics Program, Lackland AFB, Texas. Subjects who meet the eligibility requirements listed below will be offered the opportunity to participate in the study. If the subject agrees to participate, they will complete an informed consent.

12.2 Age Range:

Check all the boxes that apply. If the age range of potential subjects (specimens, records) does not match the range(s) selected, please specify in the text box.

- ☐ 0-17
- ☒ 18-24
- ☒ 25-34
- ☒ 35-44
- ☒ 45-54
- ☒ 55-64
- ☒ 65-74
- ☒ 75+

18-99

12.3 Gender:

- ☒ Male
- ☒ Female
- ☐ Other

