12.4 Special categories, check all that apply

- ☐ Minors /Children
- ☐ Students
- ☐ Employees - Civilian
- ☐ Employees - Contractor
- ☐ Resident/trainee
- ☐ Cadets /Midshipmen
- ☒ Active Duty Military Personnel
- ☐ Wounded Warriors
- ☐ Economically Disadvantaged Persons
- ☐ Educationally Disadvantaged Persons
- ☐ Physically Challenged (Physical challenges include visual and/or auditory impairment)
- ☐ Persons with Impaired Decisional Capacity
- ☐ Prisoners
- ☐ Pregnant Women, Fetuses, and Neonates
- ☐ Non-English Speakers
- ☐ International Research involving Foreign Nationals - Headquarters Review is necessary

You must also consider the requirements of DoDI 3216.02, Enclosure 3, paragraph 7.e.

12.5 Inclusion Criteria:

Order Number	Criteria
1	
 1. Age 18-99 2. Require a mucogingival periodontal surgery procedure 3. Have not taken antibiotics for one month 4. Are planned for non-emergent periodontal surgery 5. Are American Society of Anesthesiologists (ASA) Class I, II, III

12.6 Exclusion Criteria:

Order Number	Criteria
1	
 1. <18 years old, > 100 years of age 2. Currently pregnant or within 6 months postpartum 3. Female subjects who are nursing 4. Subjects who are decisionally challenged 5. ASA Class IV 6. Have undergone antibiotic therapy within one month prior to enrollment 7. Have undergone chronic therapy within one month prior to enrollment with medications that could affect periodontal status or healing. 8. Incompatible mobile device

13.0

Recruitment and Consent

13.1 Please describe the recruitment process, including how subjects will be identified and selected for the study.

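### Section 11.1 plans subgroup analyses on nine factors in 80 subjects at p < 0.05, with no interaction term, exploratory label or multiplicity control, and 10.2 does not name five of the conditions

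*Combined protocol and SAP*

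**What the plan says.** Section 11.1 commits to the analyses: "Subgroup analyses will be conducted in subjects with the following conditions: anxiety or depressive medications, smoking, sleep apnea, pulmonary disease, diabetes, autoimmune disorders". The rest of the sentence adds chronic pain management and then age and sex, making seven conditions plus two demographic factors. It names no outcome, test, subgroup definition, age cut-point or minimum size. The same section sets one significance threshold, p < 0.05, with no adjustment. It also plans an adjusted linear regression relating QoL, sleep quality, healing and intervention use, without listing covariates or interactions.

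Section 10.2 lists what will be noted from the coded medical history. Besides treatment group, it gives "type of surgery, type of sedation, experience level of clinician, length of surgery, size of harvest, smoking, diabetes", and it records age and sex separately. Smoking and diabetes are therefore the only two of the seven conditions named. The five not named are anxiety or depression medication, sleep apnea, pulmonary disease, autoimmune disorders and chronic pain management.

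Exclusion 7 in 12.6 removes people on recent chronic therapy "with medications that could affect periodontal status or healing". Section 11.2 sets the size: "The required sample size is 80, 40 subjects will receive the standard treatment and 40 the experimental intervention". Under 10.1 the arms are formed by randomization ("test group selected via computerized randomization scheme with allocation 1:1 ratio"), and no stratification factor is mentioned. Section 11.6 repeats the analysis paragraph without the subgroup sentence and ends: "Any additional data collection or analyses will be determined in coordination and consultation with other investigators and biostatistician".

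**The concern.** A p-value obtained only in smokers, or only in subjects with sleep apnea, tests whether the arms differ within that group. It does not test whether the effect there differs from the effect in everyone else, which is the usual reason for a subgroup analysis. In a trial of 80 most of these groups will be small, so a real effect will usually be missed. Nine unadjusted looks also leave a fair chance that something crosses 0.05 by accident. Without an exploratory label, such a result could be reported on the same footing as the main comparison.

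The second problem is traceability. For five conditions the plan promises an analysis but names no recorded variable. Section 10.1 makes SQI the primary outcome. As a matter of judgement, since the documents give no data on it, sleep apnea, psychotropic medication and chronic pain are likely to relate to sleep quality. They may be worth more as baseline covariates than as subgroups, but only if they are defined and recorded at baseline.

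**Working it through.** **1. Counts.** 7 conditions + age + sex = 9 factors. Smoking, diabetes, age and sex are in 10.2, so 9 − 4 = 5 are not named there.

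**2. The plan's own figure.** Section 11.2 says 80 was chosen "to provide a power of 80%, false positive rate of 5%, a 10% margin of error, and a 10% calculated dropout rate". The dropout step is consistent: 36/0.9 = 40 per arm and 72/0.9 = 80. The 72 cannot be reproduced, because no effect size, SD or event rate is given and the margin of error is not tied to a quantity.

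**3. Assumed effect.** I therefore solved for the standardized difference that gives 80% power at two-sided 5% with 36 per arm. By normal approximation it is (1.96 + 0.84) × √(2/36) = 0.66; with the t distribution it is 0.67. I use d = 0.67. It is an assumption, chosen so that the main comparison is adequately powered.

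**4. Assumed prevalence.** None is given, so I show a range. Subgroup size is 72 × prevalence, split equally and rounded.

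**5. Within-subgroup power.** Two-sided t-test with n per arm: df = 2n − 2, noncentrality d/√(2/n). The 95% CI half-width is t(0.975, df) × √(2/n) in SD units.

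**6. Interaction power.** With subgroup fraction q, the interaction standard error is √(4/(72q) + 4/(72(1 − q))). This is 1/√(q(1 − q)) times the main-effect standard error: 3.3 times at q = 0.1 and 2.0 times at q = 0.5. Power to detect a difference of 0.67 SD between subgroup effects is Φ(0.67/SE − 1.96).

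| Prevalence | Evaluable | Per arm | Within-subgroup power | Effect needed for 80% power | 95% CI half-width | Interaction power |
|---|---|---|---|---|---|---|
| 10% | 7.2 | 4 | 13% | 2.38 SD | 1.73 SD | 13% |
| 20% | 14.4 | 7 | 21% | 1.63 SD | 1.16 SD | 21% |
| 30% | 21.6 | 11 | 32% | 1.26 SD | 0.89 SD | 26% |
| 50% | 36 | 18 | 50% | 0.96 SD | 0.68 SD | 29% |

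With no dropout (40 per arm), 10%, 20% and 50% prevalence give 4, 8 and 20 per arm and power of 13%, 24% and 54%. The picture does not change.

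**7. Groups too small to test.** With 36 per arm and prevalence p, the chance that one arm has fewer than 2 such subjects is r = (1 − p)^36 + 36p(1 − p)^35. The chance that at least one arm does is 1 − (1 − r)². That is 21% at p = 10% and 70% at p = 5%.

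**8. False positives.** If the tests are independent and there is no true effect, 1 − 0.95⁹ = 37% for nine tests on one outcome. If each factor were tested on SQI, QoL and healing, 1 − 0.95²⁷ = 75%. Subgroups share subjects and outcomes are correlated, so the actual rates would usually be lower.

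**The case against.** The strongest reply is that 11.1 does not state the method. It never says that the arms are compared by a separate test in each group, and the planned regression, run with a biostatistician, could carry interaction terms. This stands in part. The separate-test reading is natural for the seven conditions because the wording confines the analysis to people who have them. It does not fit age and sex, so the documents do not support calling all nine within-subgroup tests. If interactions were intended, the plan needs to say so.

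A reader might also infer that the five conditions will not be collected. The documents do not show that. Section 10.2 says medical history will be coded and refers to a data collection sheet that is not reproduced. Section 10.9 names MHS Genesis as a source, 10.14 says the ring application tracks sleep apnea, and further data collection is left open. What stands is narrower: the five are not named in 10.2, and no definition links them to a study variable.

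Two other strong readings fail. Exclusion 7 names no drugs, so it may thin some groups, such as autoimmune disease or chronic pain, but it cannot be said to do so, nor by how much. Section 11.6 does not contradict 11.1. It leaves the subgroup sentence out, and its form prompt, unlike that of 11.1, does not ask for subgroups.

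Finally, interaction tests have low power here too, as the table shows. That is correct, and it is why the remedy is estimation under an exploratory label rather than a different set of tests.

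**Conclusion.** The concern holds in this form: nine subgroup factors are planned at p < 0.05 with no interaction term, exploratory label or multiplicity control, and five of the seven conditions have no named variable in 10.2. On the assumed d = 0.67 and prevalences of 10%, 20% and 50%, within-subgroup power is about 13%, 21% and 50%, and the chance of at least one false positive is 37% for nine independent tests on one outcome. The exact figures depend on these assumptions, but the direction does not: even an evenly split factor such as sex reaches only about half power. A smaller true effect would make matters worse. The main comparison of the arms is not affected. What is at risk is any claim that L-PRF works better or worse in a particular kind of patient.

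**What to change.** In 11.1, replace the within-subgroup tests with arm-by-factor interaction terms in the adjusted linear regression already planned. Limit them to a short pre-specified list: age as a continuous variable, sex, and smoking only if numbers allow. Fix the minimum count for smoking before outcome data are examined. Name the outcome, label the results exploratory, and report estimates with confidence intervals rather than significance calls. Describe sparse conditions by arm without testing.

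In 10.2, add and define as baseline items those unlisted conditions that the plan keeps, taken from the medical history already being coded. If the ring is to supply sleep apnea status, say so and use the pre-operative nights only. Name which of these items are pre-specified covariates for SQI, and keep the set small given about 72 evaluable subjects. Carry the same subgroup text into 11.6.

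The cost is some plan wording, a few more baseline items and fewer subgroup claims. No extra subjects or visits are needed. The change does not add power; it makes the reported results match what 80 subjects can support.
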